Study Protocol

A comparison of pain perception using topical EMLA cream versus lidocaine injection for vulvar biopsy: a randomized controlled trial

NCT03654417

Study Protocol approved September 23, 2019

Research Abstract

The purpose of this study is to compare pain control during vulvar biopsy following either (1) application of EMLA (a eutectic mixture of local anesthetics lidocaine 2.5% and prilocaine 2.5%) cream or (2) injection of 1% lidocaine.

Subjects recruited from the Duke Gynecology Oncology clinic and the Duke Womens Cancer Care Raleigh clinic who will be receiving a vulvar biopsy will be randomized to receive either EMLA cream or injectable lidocaine in preparation for the biopsy. Subjects will complete a baseline survey, and sociodemographic information will be collected. Pain will be assessed using a 100 mm visual analog scale: at baseline, after application of EMLA or lidocaine injection, and immediately after vulvar biopsy. Subjects will then complete an exit survey on their perception of the tolerability and acceptability of the procedures. The primary outcome is highest subjective pain score. We hypothesize that lidocaine will provide better biopsy analgesia, but the benefit will be offset by the pain of lidocaine injection compared to EMLA application, thus there will not be a significant difference in highest pain scores between the two groups. Subjects will be compensated \$20 for their participation.

We chose a 16-mm difference on a standard 100-mm visual analog pain scale as value of clinical significance. In order to detect at least a 16-mm difference with 90% power and alpha of .05, we estimated a total sample size of 53. Highest mean pain scores between anesthetic methods will be compared as the primary outcome using T-test vs Wilcoxon Rank sum test. Patient perception of tolerability and acceptability of the procedure as well as the provider's satisfaction with the procedure will also be analyzed. There are no additional risks/benefits to the study participant for being part of the study as both methods of anesthesia are considered standards of care.

Primary Objectives

To compare highest subjective pain score with application of EMLA cream versus injection of lidocaine for analgesia for vulvar biopsy.

Secondary Objectives

To compare pain scores at vulvar biopsy

To investigate possible pathologic changes associated with EMLA cream administration

Purpose

We hypothesize that lidocaine will provide better biopsy analgesia, but the benefit will be offset by the pain of lidocaine injection compared to EMLA application, thus there will not be a significant difference in highest pain scores between the two groups.

Background and Significance

Performing minor procedures in-office is essential to gynecologic practices.In-office procedures allow for evaluation and diagnosis of a variety of conditions while avoiding the expense, anesthesia, and time associated with the operating room.Pain and discomfort are frequently associated with these procedures, and ensuring that the patient has the least amount of discomfort is a priority.Very painful or uncomfortable procedures could potentially discourage a patient from returning to clinic or receiving the follow up that they may need.Psychological, physiologic, and social factors influence a patient's experience of pain.Previous studies, though mostly related to first trimester abortion procedures in the office, indicate that the procedure type, anxiety, depression, and general anticipation of pain predict increased pain during in office gynecologic procedures (1-4).A review by Ireland et al., found that a multimodal approach that includes patient counseling with other techniques is most effective in achieving optimum pain control for procedures (5,6).

Vulvar biopsies are associated with significant discomfort, and some form of anesthesia is required. The current standard in our group is to inject local anesthesia prior to vulvar biopsy. However, the injection itself is associated with its own level of pain that is not insignificant, and for many, the anticipation of receiving an injection is anxiety provoking. The use of topical anesthesia in lieu of injection or as pre-injection analgesia is variable.

Several previous studies have examined the use of topical anesthetics in the place of or in addition to injected anesthesia.Drouault et al. compared EMLA cream alone to injected lidocaine alone for pain relief in vulvar biopsy and found that pain associated with administration of anesthesia was significantly less for EMLA cream, but better biopsy analgesia was obtained with injected anesthesia.The study considered combined pain scores for both groups for the overall procedure (anesthesia + biopsy), it comments that the combined scores were lower for the EMLA group but failed to reach statistical significance. The study ultimately concluded that EMLA is the less painful procedure to obtain anesthesia and that it can be used as an alternative to injection for biopsies of the genital mucosa (7). This prior study did not compare the highest pain score between groups.Consideration of the highest pain score allows us to assess whether the injection of lidocaine could result in causing more pain than the biopsy itself using EMLA cream alone for anesthesia.Further, the study did not assess the subjects' or the providers' perception of the tolerability and acceptability of performing the procedure using either method.This is an important factor in any in office procedure

EMLA cream is the most extensively studied topical anesthetic.It is FDA approved for use as a topical anesthetic on the genital mucous membranes for superficial, minor surgery.EMLA cream requires between 7-10 minutes of absorption time on the genital mucosa for analgesic effect, with variable duration of analgesia following, usually around 15-20 minutes (9).There is a highly variable absorption rate for EMLA cream depending on the characteristics of the epithelium upon which it is applied as well as the duration and surface area of cream applied.On hair-bearing non-mucosal surfaces it can require 60 minutes of application time to obtain analgesic affect (10).The vulvar area is unique in that it contains both mucosal and non-mucosal and hair-bearing surfaces; this could greatly affect the absorption of EMLA and therefore affect analgesia.For this reason, we will exclude from the study patients requiring vulvar biopsy on hair bearing portion of the vulva.

There have been case reports of EMLA induced pathologic changes in children with a variety of inflammatory skin conditions where disruptive changes on H&E were noted. Similarly in a small series of patients with vulvar dermatoses, EMLA was associated with similar disruptive changes on H&E. The extent of these changes and their ability to impact pathologic diagnoses have not been studied.

Design and Procedures

Following informed consent enrollment, subjects will be randomized to an arm of the study using the randomization tool in REDCap. eConsent will be programmed in REDCapand. Study subjects, study staff, and performing providers will not be blinded to the intervention as the interventions are different; therefore, our study design is an unblinded randomized controlled trial.Selection criteria are listed in the table below.

Selection Criteria

Participant Inclusion Criteria	Participant Exclusion Criteria
 Females above age 18 presenting to Duke Gynecology Oncology clinic for vulvar biopsy Able to provide informed consent in English and agree to the risks of the study 	 a. Not able to provide informed consent b. Vulvar biopsy on a hair bearing surface

It is not standard to perform pregnancy testing prior to vulvar biopsy in Duke Gynecology Oncology clinic and Duke Womens Cancer Care Raleigh clinic as the administration of anesthesia and procedure itself present minimal risk of harming a fetus. Both EMLA cream and injected lidocaine are labeled pregnancy category B indicating that reproduction studies performed in rats have revealed no evidence of harm to the fetus, but there are no adequate and well-controlled studies in pregnant women (10, 14). For these reasons, we will not perform pregnancy tests on possible study participants.

Because participation in the study only lasts the duration of the clinic visit during that day, and EMLA and lidocaine are pregnancy category B, there are no specific contraceptive methods required preceding or following participation in the study.

Measurement of anxiety, acceptability, and pain

Before the procedure is performed, subjects will complete the GAD-7, a validated 7 item anxiety disorder scale(15).

Subjects will report pain using a visual analog scale, a scale comprised of a 100 mm horizontal line anchored with 2 verbal descriptors, one for each symptom extreme. For pain, the scale is most often anchored by "no pain" (score of 0) and "worst imaginable pain" (score of 100 mm). The patient marks their pain with a vertical line perpendicular to the scale, and the distance from 0 is measured with a ruler (16-18).

Subjects will also be asked to rate the overall acceptability and tolerability of the procedure performed with a visual analog scale. The provider performing the biopsy will rate their overall satisfaction and perception of patient tolerability of the procedure using the same scale. The subjects will also be asked if the procedure was better or worse than they expected.

Study Procedures:

Intake information: Patients will present to their scheduled Duke Gynecology Oncology Clinic or Duke Womens Cancer Care Raleigh clinic appointment. If it is determined that a vulvar biopsy is indicated, the provider will briefly inquire about interest in the study. If interested, a study coordinator will introduce the study to the patient and perform informed consent should they decide to participate. After providing informed consent, the patient will complete a survey including sociodemographic information and a baseline anxiety survey (GAD7) (see appendices). The following information will be collected: age, race, ethnicity, level of education, baseline vulvar pain using a 100 mm visual analog scale, history of previous vulvar biopsy, daily narcotic or anxiolytic use. Information including BMI, chronic pain diagnoses, history of vulvar cancer will be collected by study coordinators from the medical record.

Participants will complete questionnaires electronically with the exception of the pain assessment by visual analog scale. The data will be collected directly into REDCap. Pain scores will be entered into REDCap by measuring from 0 millimeters the hash mark made by the patient. There will be paper forms of the questionnaires available, as a secondary option should it become necessary.

Randomization: After completing the entry intake information, the subject will be randomized to EMLA cream application or lidocaine injection using the randomization tool within REDCap

Procedure: The subject will then be placed in dorsal lithotomy position on the Gynecology Oncology pelvic exam tables in preparation for the procedure. If the patient is randomized to the EMLA cream group, the EMLA cream will be applied at the intended site of biopsy and left in place for a minimum of 10 minutes prior to biopsy. Approximately 5 g of EMLA should be applied in a thick layer to the area to be biopsied (a 1g strip is approximately 1.5 x 0.2 inches and squeezed from the tube in a narrow strip) (10). The subject will report a pain score at time of EMLA application. After 10 minutes vulvar biopsy will be performed.

For subjects receiving lidocaine injection, approximately 2 mL of 1% lidocaine will be injected superficially at the planned biopsy site using a 25- or 27-gauge needle at the discretion of the physican. The subject will report pain at time of injection on a 100 mm visual analog scale before proceeding to vulvar biopsy. The provider will then wait at least one minute after lidocaine injection before performing the biopsy.

In both arms, should the provider deem anesthesia to be inadequate prior to performance of the biopsy, an additional lidocaine injection will be allowed prior to biopsy and this will be recorded.

Vulvar biopsies will be performed using standard biopsy forceps or a punch biopsy (3-4 mm) device depending on provider preference. The subject will report pain using a 100 mm visual analog scale immediately following biopsy.

If there are multiple biopsy sites that are treated, and the pain differs between these locations, the highest pain score will be recorded.

If the procedure is interrupted secondary to pain, a pain score will be recorded prior to injecting additional lidocaine, as described above.

Exit Survey: After completion of the procedure, subjects will complete an exit survey, as described above(see appendices), answering questions about overall satisfaction/tolerability of the procedure.

The provider performing the biopsy will also complete a brief survey answering questions about their satisfaction with the procedure and their perception of the acceptability of the procedure performed.

As described above, participants will complete questionnaires electronically with the exception of the pain assessment by visual analog scale, which will be completed on paper and measured distances will be entered into REDCap.

Participants will receive a \$20 check for participation in the study.All completed surveys will be collected by the study coordinator who will store the documents in a password protected file on the Duke secured server.

Post Study Pathologic Analysis: To address the concern that EMLA might induce pathologic changes that could result in altered diagnosis, pathologist independent from initial diagnostic read will re-evaluate tissue slides and look for the previously described EMLA induced pathologic changes (pallor, necrosis, spongiosis, basophilic granules, acantholysis, clefting, papillary dermal edema). Pathologist will be blinded to whether or not patient received EMLA cream for biopsy. They will provide a score for all specimens that will be used to analyse any pathologic differences between patients exposed to EMLA and those not exposed to EMLA.

Selection of Subjects

An electronic consent form will be used during the informed consent process, the signed copy of the study consent form will be emailed to the subject or printed and provided to her in clinic based on her preference. Subjects will then be assigned a unique subject number by the research coordinator. Research coordinators will maintain an enrollment log to serve as the master list for the enrolled subjects. After their information is placed into the enrollment log, the subject will only be identified by their unique number. The enrollment log as well as the study questionnaires and pain assessment forms will be collected into a REDCap data base with any exported copies saved in a password protected file on the Duke secured server.

Subject's Capacity to Give Legally Effective Consent

Subjects who do not have capacity to give legally effective consent will not be included in the study.

Risk/Benefit Assessment

There is a potential benefit for the subjects in this study in that they may receive analgesia for the procedure without the pain of an injection. However, it will be emphasized to the subject that there may be increased pain during biopsy in the EMLA arm or increased pain with injection for the lidocaine arm.

There are risks associated with vulvar biopsy including bleeding and infection. These risks are small, but they are not risks incurred as a result of participating in the study as these patients will be getting vulvar biopsies regardless of study participation.

There is a small risk of topical reaction to the EMLA cream. If irritation does occur, the area of irritation will be cleansed with water and the procedure will be postponed until the irritation is resolved. The subjects will return to clinic to assess for resolution of the area and their indicated vulvar biopsy.

Costs to the Subject

No additional costs will be incurred by the participant as a result of participating in this study

Data Analysis and Statistical Considerations

A 16-mm difference on a standard 100-mm visual analog pain scale was deemed clinically significant. In order to detect a 16-mm difference with 90% power at an alpha level of 0.05 assuming a standard deviation of 25-mm, we estimated a needed sample size of 53 participants in each treatment arm. However, due to time limitations, data collection will end on March 12, 2019. Only patients consented on or prior to March 12, 2019 will be included in the study. Data will be recorded using Research Electronic Data Capture (REDCap), and the database will be locked on March 13, 2019. Pain will be measured during the application of EMLA cream or lidocaine injection, and immediately after biopsy. The primary outcome will be the highest pain score recorded during the procedure. The primary outcome sinclude pain score at vulvar biopsy, patient tolerability and acceptability, and provider's satisfaction with the procedure. All testing will be performed at a two-tailed significance level of 0.05.

If significance for the primary objective is not achieved, then patient accrual will continue based on a new sample size determined by the primary results of this analysis. This will be the number of new patients that need to be enrolled. Outcomes will be assessed again at the point when the final sample size is achieved.

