# Table 1.1. Patient demographics and characteristics

2. Objective: Compare highest subjective pain score between patients receiving EMLA cream vs. lidocaine

**Analysis:** Linear regression will be used to test if the highest pain score differs between treatment arms, controlling for baseline pain. The regression coefficient, 95% confidence interval, and p value will be reported for the treatment effect. A significant p value would indicate that the highest pain score, on average, differed between the two treatment arms. If there is not a significant difference between treatment arms with regards to the highest pain score, then the mean and variance estimates from these patients will be used to recalculate the sample size needed (objective 3).

**Conclusions:** The highest pain score was created as the maximum between pain during application of anesthesia and pain immediately following biopsy. The median highest pain score in the EMLA cream group was 20.0 mm vs. 56.5 mm in the lidocaine injection group.

Table 2.1. Highest pain score by treatment arm					
	EMLA cream (N=19)	Lidocaine injection only (N=18)	Total (N=37)		
Highest pain score (n	nm)				
Ν	19	18	37		
Mean (SD)	26.7 (29.0)	52.5 (32.0)	39.2 (32.8)		
Median	20.0	56.5	27.0		
Q1, Q3	5.0, 50.0	26.0, 80.0	12.0, 61.0		
Range	(0.0-100.0)	(5.0-100.0)	(0.0-100.0)		

All patients in the lidocaine injection group reported having the same as or more pain during the injection than the biopsy. Four out of nineteen patients in the EMLA cream group reported more pain from the application of the cream than the biopsy, and three reported the same amount of pain.

Frequency Row Percent	More pain from biopsy	Same amount of pain	More pain from application of anesthesia	Total
Lidocaine injection only	0 0.00	1 5.56	17 94.44	18
EMLA cream	12 63.16	3 15.79	4 21.05	19
Total	12	4	21	37

From the linear regression model, patients that received EMLA cream were expected to report their highest pain score 25.7 mm lower than the lidocaine injection group (95% CI = [-45.1, -6.3], p < 0.01). In other words, the highest pain score in the EMLA cream group was significantly lower than in the lidocaine injection group.

**3. Objective:** Calculate the new sample size needed using effect estimates from the interim analysis

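### The protocol hypothesises no significant difference in highest pain, but the plan can only conclude a difference, and a non-significant first analysis leads to further accrual sized on the observed difference

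*Protocol*

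**What the plan says.** **Hypothesis.** The Protocol's Research Abstract and Purpose both predict that "thus there will not be a significant difference in highest pain scores between the two groups". The SAP does not repeat this. In both documents the primary objective is framed only as a comparison of the arms.

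**Sizing.** Protocol, Data Analysis and Statistical Considerations: "A 16-mm difference on a standard 100-mm visual analog pain scale was deemed clinically significant". The 16 mm serves as a difference to detect, and "we estimated a needed sample size of 53 participants in each treatment arm".

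**Test.** "All testing will be performed at a two-tailed significance level of 0.05". The Abstract names a t-test or Wilcoxon test. SAP Objective 2 uses linear regression adjusted for baseline pain and reports a 95% CI. It interprets one outcome only: "A significant p value would indicate that the highest pain score, on average, differed between the two treatment arms".

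**After a non-significant result.** "If significance for the primary objective is not achieved, then patient accrual will continue based on a new sample size". SAP Objective 3 sets that size from the observed difference and SD, at 90% power, and counts new patients only. The protocol says outcomes will then be reassessed, with no rule for a second non-significant result.

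The protocol and SAP text available contains no equivalence margin, no pair of one-sided tests and no rule that compares the CI with 16 mm.

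**The concern.** A p value above 0.05 fits the hypothesis as worded, but it is not evidence that the arms are similar: a small or noisy sample produces it whatever the truth. The SAP makes this point itself under Objective 4, for the secondary and exploratory results, but does not apply it to the primary hypothesis.

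The accrual rule adds a second problem. It treats the hypothesised result as an unfinished trial and asks for enough new patients to detect whatever difference was seen. The closer the data lie to the hypothesis, the larger the trial demanded. An investigator whose hypothesis is correct would nearly always be sent to a second stage of unpredictable and possibly unachievable size, with no rule at its end for stating the conclusion.

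**Working it through.** **Inputs.** Protocol, Data Analysis: "In order to detect a 16-mm difference with 90% power at an alpha level of 0.05 assuming a standard deviation of 25-mm", two-sided. SAP Objective 1: 19 and 18 patients. SAP Table 2.1: SDs 29.0 and 32.0, pooled as sqrt[(18 × 29.0² + 17 × 32.0²)/35] = sqrt(32,546/35) = 30.5 mm. Assumption: the documents give no equivalence margin, so 16 mm is tried and then varied. Calculations use normal data and an unadjusted comparison.

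**1. The plan's own figure.** n per arm = 2 × [SD × (1.960 + 1.282)/difference]² = 2 × (25 × 3.242/16)² = 51.3, so 52. The noncentral t gives power 0.898 at 52 and 0.904 at 53. The stated 53 per arm reproduces, as a sample size for detecting a difference. (The Abstract's "we estimated a total sample size of 53" would give about 63% power on the same inputs. That is a separate inconsistency to reconcile.)

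**2. If the hypothesis is true.** With a true difference of 0, a two-sided 5% test is non-significant about 95% of the time (0.9498 in 200,000 simulated trials at 19/18). All of these go to further accrual.

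**3. Size of that accrual.** Objective 3 gives n per arm = 2 × (s × 3.242/d)², where d is the observed difference and s the observed SD. With s = 25:

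| Observed d (mm) | New patients per arm |
|---|---|
| 16 | about 51 |
| 8 | about 205 |
| 4 | about 821 |
| 2 | about 3,284 |

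There is no upper limit. There is a lower one: non-significance at 19/18 means |d| < 2.030 × s × sqrt(1/19 + 1/18), so n is at least 2 × 3.242²/(2.030² × 0.1082), about 47 per arm. Among the simulated non-significant trials (true difference 0, SD 25) the median was 467 per arm, the quartiles were 166 and 2,076, and 49% exceeded 500.

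**4. Non-significance as evidence.** If the true difference is 16 mm, the chance of p > 0.05 is:
- 53 per arm, SD 25: 1 - 0.904 = 0.096 (10%)
- 19/18, SD 25: 1 - 0.473 = 0.527 (53%)
- 19/18, SD 30.5: 1 - 0.342 = 0.658 (66%)

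**5. What an equivalence rule could do.** The rule is two one-sided 5% tests, that is, the 90% CI wholly within ±16 mm. Power when the true difference is 0:

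| Patients | SD 25 | SD 30.5 |
|---|---|---|
| 53 per arm | 0.897 | 0.701 |
| 19/18 | 0.215 | 0.036 |

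90% power needs 54 per arm at SD 25 and 80 at SD 30.5. With a 95% CI instead, the figures are 65 and 96. At SD 25 with a 90% CI, other margins need 136 (10 mm), 95 (12 mm) or 35 (20 mm) per arm.

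At 19/18 with SD 25 the 90% CI half-width is 13.9 mm, so the estimate must lie within about 16 - 13.9 = 2.1 mm of zero. With SD 30.5 the half-width is 16.9 mm, already wider than the margin. The share of true-null trials still sent to accrual is therefore 0.9498 - 0.2150 = 0.7348 (73%) at SD 25, or 0.9498 - 0.0356 = 0.9142 (91%) at SD 30.5.

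**6. Re-sizing on 16 mm.** With the updated SD, n per arm = 2 × (30.5 × 3.242/16)² = 76.4, so 77. This is finite and does not depend on the observed difference.

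**The case against.** The strongest reply is that this is a superiority design with a loosely worded expectation attached. The objective is to compare. The background section justifies the endpoint by asking whether the injection might hurt more than a biopsy under EMLA, which is a difference question, and the sizing and test answer it. This stands. A reader might infer that the trial cannot answer its own question, but the documents do not support that. It also means that rewording the hypothesis is a sufficient cure for the mismatch.

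Second, a reader might take the 53% and 66% in step 4 as the chance of falsely confirming the hypothesis. They are not. At the first analysis the plan sends a non-significant result to further accrual and nowhere counts it as support. The figures show only how weak such a result would be as evidence.

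Third, a margin rule would seldom stop accrual at 37 patients, and nothing in the protocol says that a difference below 16 mm may be ignored. Both points stand. A margin needs its own justification, and the re-sizing rule needs repair whether or not a margin is added.

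Fourth, the data have been analysed and the non-significance branch was never entered. This also stands: a margin introduced now is post hoc for these patients.

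**Conclusion.** The mismatch is real and should be corrected. The plan has no route to the conclusion its hypothesis predicts. If the true difference is 0, about 95% of trials go to further accrual, whose size is unbounded. The 95% follows from the 5% test level alone. The median of 467 per arm rests on normal data, SD 25, group sizes of 19/18 and an unadjusted test. The equivalence figures also rest on an assumed 16-mm margin.

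A reader might infer that the flaw undermines the reported finding. It does not: the adjusted difference was -25.7 mm (95% CI -45.1 to -6.3), which was significant, and accrual stopped. That result runs against the hypothesis as worded, and the SAP's conclusions do not say so. Nor does it establish a difference beyond 16 mm, since the interval extends to -6.3.

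**What to change.** 1. **Hypothesis and conclusion rule.** Choose one of two options.
   - Restate the hypothesis in the Abstract and Purpose as a difference question, matching the test and the 16-mm sizing.
   - Prespecify in the Purpose and SAP Objective 2 that no clinically important difference is concluded only if the CI for the adjusted difference lies wholly within a justified margin. The protocol's 16 mm is the only stated candidate. Give the CI level (90% for two one-sided 5% tests) and set it beside the two-tailed 0.05 rule and the 95% CI. State that p > 0.05 is not evidence of no difference.
2. **Accrual rule.** In the protocol's Data Analysis section and SAP Objectives 2 and 3, size any further accrual on the prespecified 16 mm with the updated SD, not on the observed difference. If a margin is adopted, do not continue accrual when the CI lies within it.
3. **Reporting.** State that the present result is contrary to the protocol's hypothesis. Label any margin-based reading of the 37 patients as post hoc.

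**Cost.** These are wording changes to the protocol and SAP, with no new data or patients for the reported analysis. The margin option also needs a clinical justification. Its limit should be stated: equivalence power is about 90% at 53 per arm with SD 25, 70% with SD 30.5, and only about 22% or 4% at 19/18, so at the interim size the CI rule would rarely stop accrual.

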## **Primary Outcome**

- Pain was recorded during the application of EMLA cream or injection of lidocaine, and immediately after the biopsy on a 100 mm visual analog scale. If multiple sites were biopsied and the pain level differed between sites, then the highest pain score was recorded. If the anesthesia was inadequate in either treatment arm prior to biopsy, then an additional lidocaine injection was given and pain was recorded prior to the additional injection. The highest of all these pain measurements will be used as the primary outcome.
  - Continuous variable ranging from 0 to 100

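### No pain score is requested at a rescue lidocaine injection, so a rescued EMLA patient's highest pain omits her only injection, which may favour EMLA

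*Protocol*

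**What the plan says.** Protocol, Study Procedures (Procedure paragraphs): in both arms, if the provider finds anaesthesia inadequate, "an additional lidocaine injection will be allowed prior to biopsy and this will be recorded". If the procedure is interrupted because of pain, "a pain score will be recorded prior to injecting additional lidocaine". The lidocaine arm's first injection does have its own score: "The subject will report pain at time of injection on a 100 mm visual analog scale before proceeding to vulvar biopsy".

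SAP, Primary Outcome: when anaesthesia was inadequate, "an additional lidocaine injection was given and pain was recorded prior to the additional injection". The endpoint is then defined over the listed scores: "The highest of all these pain measurements will be used as the primary outcome". Those are pain at cream application or injection, pain after biopsy, and the score before rescue.

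SAP, Analysis Objectives, Objective 2 (Conclusions): "The highest pain score was created as the maximum between pain during application of anesthesia and pain immediately following biopsy". On the lidocaine arm it adds: "All patients in the lidocaine injection group reported having the same as or more pain during the injection than the biopsy". After adjustment for baseline pain, the EMLA group's highest score is "25.7 mm lower than the lidocaine injection group", with 95% CI -45.1 to -6.3.

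**The concern.** The protocol's Background justifies the highest-pain endpoint as a way to weigh the pain of injecting lidocaine against the pain of a biopsy under EMLA alone. An EMLA patient who needs rescue has both the cream and an injection. Her injection is not among the scores that form her maximum, and her post-biopsy score is taken after the added lidocaine.

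The gap is not symmetric. A rescued lidocaine patient's second injection is also unscored, but her first is already in the maximum. For the EMLA patient the missing injection is the only one.

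At stake is the size of the primary effect, and possibly its significance. SAP Objective 3 relies on that significance when it concludes that accrual can stop. With 37 patients, a few rescues could matter.

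**Working it through.** **1. Direction.** Adding a score to a maximum can raise it or leave it unchanged, never lower it. Leaving out the rescue score can therefore only understate a rescued patient's maximum or leave it correct, in either arm.

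**2. The reported effect.** From Table 2.1: 26.7 - 52.5 = -25.8 mm. Pooled SD = √[(18×29.0² + 17×32.0²)/35] = 30.5. SE = 30.5 × √(1/19 + 1/18) = 10.0. The unadjusted 95% CI is -46.2 to -5.4, which agrees well with the adjusted -25.7 (-45.1 to -6.3).

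**3. Model for an unscored rescue.** Inputs are the minimum, quartiles and maximum in Table 2.1, joined by straight lines: EMLA 0 / 5 / 20 / 50 / 100; lidocaine 5 / 26 / 56.5 / 80 / 100. Injection pain equalled the maximum in 18 of 18 lidocaine patients, so the second set also describes injection pain.

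Shift in the EMLA mean per rescue = {E[max(EMLA score, f × injection score)] - E[EMLA score]} / 19, where f = 1 is full intensity and f = 0.5 is half.

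- Independent scores, random EMLA patient: 30.6/19 = 1.61 mm (f = 1); 10.9/19 = 0.58 mm (f = 0.5).
- Perfect rank correlation: the lidocaine quantile exceeds the EMLA quantile everywhere below 100, so at f = 1 the gain is the difference in interpolated means, (53.75 - 31.25)/19 = 1.18 mm. At f = 0.5 it is 0.20 mm.
- Under independence the maximum does not change in 28% (f = 1) or 47% (f = 0.5) of rescued EMLA patients.

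**4. Lidocaine-arm offset.** The same formula with two injection draws, divided by 18, gives about 0.92 mm per rescue at f = 1 and 0.22 mm at f = 0.5 if independent. It is 0 under perfect rank correlation, because the second score never exceeds the first. Under independence, full cancellation would need about 1.61/0.92 = 1.75 lidocaine rescues per EMLA rescue at full intensity, or 0.58/0.22 = 2.6 at half.

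**5. Break-even.** With no lidocaine rescues and the interval width held fixed, the upper limit of -6.3 reaches 0 after 6.3 / (shift per rescue) EMLA rescues.

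| Rescued patient's recorded maximum | f = 1: mm per rescue | Rescues to reach 0 | f = 0.5: mm per rescue | Rescues to reach 0 |
|---|---|---|---|---|
| Random draw | 1.61 | 3.9 | 0.58 | 10.9 |
| Lowest quarter | 2.70 | 2.3 | 1.28 | 4.9 |
| Lower half | 2.44 | 2.6 | 1.06 | 5.9 |
| Upper half | 0.77 | 8.2 | 0.09 | more than 19 |
| Top quarter | 0.27 | more than 19 | 0.00 | never |
| Random draw, perfect rank correlation | 1.18 | 5.3 | 0.20 | more than 19 |

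At four full-intensity rescues the estimate is -25.7 + 4 × 1.61 = -19.3 mm.

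**6. Checks.** The interpolated EMLA mean (31.25) exceeds the published 26.7. Refitting the curve to 26.7 in three ways gives 1.70 to 1.75 mm (f = 1) and 0.58 to 0.65 mm (f = 0.5) per rescue. A plain shift from the EMLA mean to the lidocaine mean gives 25.8/19 = 1.36 mm per rescue; at five rescues the upper limit is -6.3 + 5 × 1.36 = +0.5.

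**The case against.** The best defence is that nothing shows harm occurred. No rescue count is given, and the pain assessment forms, which might carry a rescue score, are not in the documents. The protocol's statistics section speaks of pain during cream application or lidocaine injection, which could be stretched to cover a second injection. Needle pain in tissue already treated with EMLA may be well below that of a first injection. Patients who report more pain at one step may also do so at the next, which shrinks the gain. The lidocaine arm has the same gap in the opposite direction.

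Most of this stands, and it limits the point to a conditional one. The stretched reading is weak: the sentence asking for a score at injection belongs to the lidocaine arm's initial dose, and where the texts address rescue they place the score before it.

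A reader might infer that any EMLA rescue biases the result. It does so only if that injection exceeded every score she gave. A reader might also take the SAP's past tense as evidence that rescues took place. The sentence is conditional, and no table counts any.

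**Conclusion.** The gap is real in the text: neither document asks for a pain score at a rescue injection, and the derived endpoint uses application and post-biopsy pain only. Its effect may favour EMLA, by roughly 0.2 to 1.6 mm per EMLA rescue for a random EMLA patient, across half to full intensity and from perfectly correlated to independent scores. Lidocaine-arm rescues would offset this by 0 to 0.9 mm each. Full intensity is an upper-end assumption.

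The number of EMLA rescues needed to bring the confidence limit to zero is about 4 (full intensity, random draw) or 11 (half), within a range from about 3 to unreachable. The documents do not show which case applies.

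They do not support the stronger inference that the EMLA advantage is an artefact of unscored rescues. With no EMLA rescue there is no bias towards EMLA from this source. Even at four full-intensity rescues the estimate, about -19 mm, stays beyond the 16 mm threshold.

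**What to change.** **For the 37 analysed patients.** Report additional lidocaine injections by arm, which the protocol already requires to be recorded, and state whether pain at those injections was scored. If no EMLA patient was rescued, or the scores exist and entered the maximum, the point closes. If any EMLA rescue went unscored, add one sensitivity analysis over a range of assumed rescue-injection scores, for example half to full lidocaine-arm intensity. Apply it to rescued patients in both arms, replacing a maximum only when the assumed score is higher. The missing VAS marks cannot be recovered, so this analysis will rest on assumptions.

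**For further accrual or reuse.** In the protocol's Study Procedures, take a VAS score at any additional lidocaine injection. In the SAP's Primary Outcome, include that score in the maximum in both arms. When rescue is allowed need not change.

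**Cost.** Now: one line of counts and, conditionally, one analysis. Later: one VAS mark per rescued patient and one SAP sentence. The EMLA benefit may turn out smaller.
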